Appendix 6. Hypoglycemic Clamp Procedure

The patient will be asked to attend the clinical unit at approximately 18:00 hours in the evening of Day 79 of each treatment period. The patient will be served a standardized dinner at approximately 19:00 hours and thereafter will be fasted until the end of the clamp procedure on Day 80. The clamp procedure will be initiated on Day 79 (clamp run-in period) and the hypoglycemic induction will be performed on Day 80 of each period.

Invasive procedures

For sampling of arterialized venous blood, a hand or antecubital vein of one arm will be cannulated. This hand will remain in a heating environment throughout the procedure. The heating of the hand results in an arterialization of the venous blood due to a reflective opening of arteriovenous shunts. The patency of the cannulation will be maintained with a 154 mmol/L NaCl infusion throughout the procedure.

An antecubital vein in the contralateral arm will be cannulated for the infusion of human soluble insulin and/or glucose 20%.

Clamp Run-in period

At approximately 22:00 hours in the evening of Day 79, a variable intravenous (IV) infusion of human soluble insulin (40 IU insulin lispro [100 IU/mL] in 99.6 mL saline) or a variable IV infusion of glucose will be initiated in order to obtain a plasma glucose (PG) target level of 100 mg/dL (5.5 mmol/L). The insulin infusion should be stopped completely if glucose has to be infused and vice versa. The rates of the variable glucose infusion will be recorded whenever the infusion rate is changed (at least every 30 minutes). The insulin infusion rate needed until initiation of the high constant insulin infusion will also be recorded whenever the infusion rate is changed (at least every 30 minutes).

Between 07:00 hours and 08:00 hours on Day 80, PG should be stable at 100 mg/dL (5.5 mmol/L) $\pm 30\%$ and no glucose should be infused. In case this PG target range of 100 mg/dL (5.5 mmol/L) $\pm 30\%$ cannot be achieved, this period can be extended until 10:00 hours.

At 08:00 hours (10:00 hours latest), the insulin infusion rate will be increased to a constant rate of 2.5 mU/kg/min, based on patient body weight at Day 78 of each period.

Hypoglycemic induction

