A PG target level of 100 mg/dL (5.5 mmol/L) $\pm 30\%$ should be kept constant from 60 minutes to 30 minutes prior to hypoglycemia induction by a controlled variable glucose infusion. Moreover, the PG target level of 100 mg/dL (5.5 mmol/L) $\pm 10\%$ should be kept constant for the last 30 minutes prior to hypoglycemia induction while performing all assessments of plateau 100 mg/dL (5.5 mmol/L).

Hypoglycemic induction is defined as stop of glucose infusion after assessment plateau 100 mg/dL (5.5 mmol/L) is completed.

After 30 minutes (09:00 hour) on the 100 mg/dL (5.5 mmol/L) assessment plateau, the glucose infusion will be interrupted, the PG will be allowed to decline to 63 mg/dL (3.5 mmol/L) and by restarting a variable glucose infusion, if needed, kept stable at 63 mg/dL (3.5 mmol/L). Assessments on the assessment plateau 63 mg/dL (3.5 mmol/L) will be performed.

After 30 min on the 63 mg/dL (3.5 mmol/L) assessment plateau, the glucose infusion will be interrupted and the PG will be allowed to decline to 45 mg/dL (2.5 mmol/L) or nadir at a higher PG concentration in case 45 mg/dL (2.5 mmol/L) cannot be reached or symptoms of hypoglycemia are unacceptable. By restarting a variable glucose infusion, if needed, the PG will be kept stable at 45 mg/dL (2.5 mmol/L) or nadir, and assessments on the 45 mg/dL (2.5 mmol/L) or nadir assessment plateau, will be performed.

As soon as the 45 mg/dL (2.5 mmol/L) or nadir assessment plateau has been reached, the constant high insulin infusion will be terminated. The 45 mg/dL (2.5 mmol/L) or nadir plateau will be further kept, if possible, for the total duration of 30 min.

Recovery phase

After, at the latest, 30 minutes' duration of the 45 mg/dL (2.5 mmol/L) or nadir assessment plateau, the glucose infusion will be switched off to allow a spontaneous recovery from hypoglycemia.

The PG will not be allowed to fall below 40 mg/dL (2.2 mmol/L), if so, the variable glucose infusion will be initiated to raise the PG to 45 mg/dL (2.5 mmol/L).

If the PG has not reached ≥ 72 mg/dL (4.0 mmol/L) 45 minutes after termination of the constant insulin infusion, a constant glucose infusion (5.5 mg/kg/min, based on patient body weight at Day 78 of each period) will be initiated in order to increase the PG to 72 mg/dL (4.0 mmol/L). For medical reasons (e.g., if symptoms of hypoglycemia are unacceptable) the constant glucose infusion can be initiated earlier as judged by investigator.

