As soon as PG 72 mg/dL (4.0 mmol/L) is reached, assessments on the recovery time point will be performed. When the assessments are finished, PG will actively be raised to 100 mg/dL (5.5 mmol/L) by a variable glucose infusion and the whole clamp procedure terminated when deemed safe by the investigator. Thereafter, patients will receive a meal (containing carbohydrates) and will be discharged after having achieved stable medical conditions, as judged by the investigator.

Safety considerations for assessment plateaus

In case a patient's PG does not decrease from 100 mg/dL (5.5 mmol/L) to 63 mg/dL (3.5 mmol/L) within 30 minutes, the 63 mg/dL (3.5 mmol/L) assessment plateau will be initiated in any case 30 minutes after the end of the assessment plateau at 100 mg/dL (5.5 mmol/L).

In case a patient's PG does not decrease from 63 mg/dL (3.5 mmol/L) to 45 mg/dL (2.5 mmol/L) within 30 minutes, the 45 mg/dL (2.5 mmol/L) assessment plateau will be initiated in any case 30 minutes after the end of the assessment plateau at 63 mg/dL (3.5 mmol/L).

In the above cases, the glucose infusion should not be initiated at the start of the assessment plateaus to allow a further decrease in PG levels to the scheduled target PG levels.

Based on the clinical judgement of the investigator, the PG can be increased to euglycemia by a variable glucose infusion at any time during the whole clamp procedure.

From the start of the constant high insulin infusion rate until end of the recovery phase, PG measurements (using SuperGL device) have to be performed every 5 to 30 minutes or more often as judged by investigator.

After initiation of the constant high insulin infusion rate, potassium concentration will be measured at the discretion of the investigator and potassium substituted if necessary.

Electrocardiogram will be continuously monitored from start of the constant high insulin infusion rate until completion of the recovery phase. Twelve-lead ECG will be recorded within 15 minutes prior to start of the high insulin infusion rate, at timepoint 15 minutes (± 5 minutes) of assessment plateau 45 mg/dL (2.5 mmol/L) or nadir assessment plateau and before discharge.

The clamp will be terminated for safety reasons should the patient experience symptoms of cardiovascular stress (tachycardia, bradycardia, or other relevant changes in ECG), or neurological symptoms related to neuroglycopenia, as judged by the investigator.

[figure not shown]

Figure GPHG.2 Hypoglycemic clamp

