Abbreviations: PG = plasma glucose.

Glucagon, fasting insulin, C-peptide, cortisol, growth hormone, adrenaline, and noradrenaline measured at 10, 20 and 30 minutes of each clamp plateau and once PG 72 mg/dL (4.0 mmol/L) is reached.

Blood pressure and pulse rate measured at 0 and 30 minutes of each plateau and once PG 72 mg/dL (4.0 mmol/L) is reached.

Hypoglycemic symptom score and hypoglycemic symptom awareness assessed at 0 and 30 minutes of each plateau and once PG 72 mg/dL (4.0 mmol/L) is reached.

Approximate hour	Nominal timing	Procedure	Clamp glucose level	Blood sampling: - Glucagon - Fasting insulin - C-peptide - Growth hormone - Cortisol - Adrenaline - Noradrenaline	Hypoglycemia symptoms awareness Hypoglycemic symptoms score	Vital signs and ECG	Glucose and GIR recorded
				glucagon at ambient PG sample taken in pre-prandial state prior to clamp initiation			
22:00	-11 hours	Start run-in period: variable infusion of glucose or insulin lispro (40 IU [100 IU/mL] in 99.6 mL saline) targeting PG 100 mg/dL (5.5 mmol/mL) ($\pm 30\%$)	100 mg/dL (5.5 mmol/L)				Glucose every 30 minutes GIR at least every 30 minutes and every time GIR is changed until time M
7:00	-2 to -1 hours	Variable insulin infusion, no glucose infusion, targeting PG 100 mg/dL (5.5 mmol/L) ($\pm 30\%$)	100 mg/dL (5.5 mmol/L)				Glucose every 5 to 30 minutes or more often as judged by investigator
8:00	-1 hours to -30 minutes	Increase insulin flow (2.5 mU/kg/min) Variable infusion of glucose targeting PG 100 mg/dL (5.5 mmol/L) ($\pm 30\%$)	100 mg/dL (5.5 mmol/L)			Start of continuous ECG measurement	Glucose every 5 to 30 minutes or more often as judged by investigator

Approximate hour	Nominal timing	Procedure	Clamp glucose level	Blood sampling: - Glucagon - Fasting insulin - C-peptide - Growth hormone - Cortisol - Adrenaline - Noradrenaline	Hypoglycemia symptoms awareness Hypoglycemic symptoms score	Vital signs and ECG	Glucose and GIR recorded
8:30	-30 minutes	Insulin flow (2.5 mU/kg/min). Variable infusion of glucose to maintain PG 100 mg/dL (5.5 mmol/L) ($\pm 10\%$)	100 mg/dL (5.5 mmol/L)	-20 minutes, -10 minutes, 0 minutes	-30 minutes 0 minutes	Vital signs -30 minutes 0 minutes 12-lead ECG -15 minutes	Glucose every 5 to 10 minutes or more often as judged by investigator
9:00	0 minutes	Start of hypoglycemic induction. Terminate glucose infusion					Glucose every 5 minutes or more often as judged by investigator until Timepoint K

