	I minutes	PG 63 mg/dL (3.5 mmol/L) reached Variable glucose infusion if needed to maintain PG 63 mg/dL (3.5 mmol/L)	63 mg/dL (3.5 mmol/L)	I + 10 minutes I + 20 minutes I + 30 minutes	I min I + 30 minutes	Vital signs I min I + 30 minutes	
	I + 30 minutes	Terminate glucose infusion					
	J minutes	PG 45 mg/dL (2.5 mmol/L) or nadir reached Variable glucose infusion started, if needed, to maintain PG 45 mg/dL (2.5 mmol/L) or nadir Terminate insulin infusion	45 mg/dL (2.5 mmol/L)	J + 10 minutes J + 20 minutes J + 30 minutes	J minutes J + 30 minutes	Vital signs J minutes J + 30 minutes 12-lead ECG J + 15 minutes	
	J + 30 minutes	Switch off glucose infusion (infusion will restart if PG falls below 40 mg/dL until 45 mg/dL is reached)					

Approximate hour	Nominal timing	Procedure	Clamp glucose level	Blood sampling: - Glucagon - Fasting insulin - C-peptide - Growth hormone - Cortisol - Adrenaline - Noradrenaline	Hypoglycemia symptoms awareness Hypoglycemic symptoms score	Vital signs and ECG	Glucose and GIR recorded
	$J + 45$ minutes	Start of constant glucose infusion (5.5 mg/kg/min) until PG ≥ 72 mg/dL (4.0 mmol/L) is reached					
	K minutes	Time of recovery: PG reaches 72 mg/dL (4.0 mmol/L) Start variable glucose infusion	≥ 72 mg/dL (4.0 mmol/L)	K minutes	K minutes	Vital signs K minutes	Glucose every 5 to 30 minutes or more often as judged by investigator
	M minutes	PG reaches 100 mg/dL (5.5 mmol/L). End of clamp. Blood glucose controlled with insulin infusion. Patient served a meal				End of continuous ECG 12-lead ECG prior to discharge	

Abbreviations: ECG = electrocardiogram; GIR = glucose infusion rate; I = time at which PG 63 mg/dL (3.5 mmol/L), or 30 minutes after the end of the 100 mg/dL (5.5 mmol/L) assessment plateau, whichever is sooner; J = time at which PG 45 mg/dL (2.5 mmol/L), or 30 minutes after the end of the 63 mg/dL (3.5 mmol/L) assessment plateau, whichever is sooner; K = time at which PG reaches 72 mg/dL (4.0 mmol/L); M = time at which PG reaches 100 mg/dL (5.5 mmol/L) at the end of the clamp; PG = plasma glucose.

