Based on the clinical judgement of the investigator, PG can be increased to euglycemia by a variable glucose infusion at any time during the clamp procedure. The insulin infusion rate will be recorded whenever the infusion rate is changed (at least every 30 minutes). The end time of each clamp step, time to reach each plateau, and PG achieved at each plateau will be recorded. Glucose infusion rates will also be captured.

Symptoms of hypoglycemia will be measured using the Edinburgh Hypoglycemia Scale and hypoglycemic awareness will be evaluated based on the patients' response (yes/no) to the question "Do you feel hypoglycemic?".

The assessments scheduled for the same time point on each plateau will be performed in following order (priority): blood glucose, vital signs, blood sampling, hypoglycemia symptoms awareness, hypoglycemic symptoms score. The exact timing of each procedure will be recorded.

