6.9.2.3. Exploratory Pharmacodynamic Analysis

AUC will be calculated using trapezoidal rule. See Section [6.9.1](#) for data collection and calculation details.

Additional hypoglycemic clamp and recovery parameters

Insulin infusion related parameters

The human soluble insulin lispro (40 IU insulin lispro [100 IU/mL] in 99.6 mL saline) is used for intravenous infusion (insulin 40 IU/100 mL). Between 0 minutes [Stop plateau 5.5 mmol/L], I minutes [Start plateau 3.5 mmol/L], and J minutes [Start plateau nadir, Stop constant insulin infusion], insulin is infused at a constant flow 2.5 mU/kg/min, based on the patient body weight at Day 78 predose of each period. Insulin infusion is terminated once PG reaches nadir 45 mg/dL.

Unit conversion of insulin infusion rate (IIR) [mL/hour] to IIR [mU/min/kg]:

$IIR [mL/hour] * concentration 0.4 \text{ IU/mL} * 1000 \text{ mU/IU} \div (60 \text{ min/hour}) \div \text{body weight [kg]}$

Exploratory PD measures to assess the effect of tirzepatide 15 mg versus placebo on the amount insulin needed include:

- Amount of insulin [i.e. AUC of IIR; mU/kg] required to reach PG concentration of 63 mg/dL (3.5 mmol/L) from 100 mg/dL (5.5 mmol/L)
 - The time interval from Stop plateau 5.5mmol/L (0 minutes) to Start plateau 3.5mmol/L (J minutes) is of interest, where insulin is infused at a constant rate.
- Amount of insulin [i.e. AUC of IIR; mU/kg] required to reach PG concentration of nadir 45 mg/dL (2.5 mmol/L) from 100 mg/dL (5.5 mmol/L)
 - The time interval from Stop plateau 5.5mmol/L (0 minutes) to Start plateau Nadir (J minutes) is of interest, where insulin is infused at a constant rate.

Glucose infusion related parameters

The glucose 20% (200 mg/mL) is used for intravenous infusion. At J minutes [Start plateau nadir, Stop constant insulin infusion], variable glucose infusion started, if needed to maintain nadir PG 45 mg/dL. At J+30 minutes [Stop plateau nadir, Start recovery], glucose infusion if switched off, and will be restarted if PG falls below 40 mg/dL until 45 mg/dL is reached. At J+45 minutes, if PG doesn't recover to 72 mg/dL, constant glucose infusion flow (5.5 mg/kg/min) is started [Start constant glucose infusion] until PG $\geq 72 \text{ mg/dL}$ (at K minutes: Timepoint 4.0 mmol/L reached), based on the patient body weight at Day 78 predose of each period.

Unit conversion of glucose infusion rate (GIR) [mL/hour] to GIR [mg/min/kg]:

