$GIR [mL/hour] * concentration 20 \text{ g/100 mL} * 1000 \text{ mg/g} \div (60 \text{ min/hour}) \div \text{body weight [kg]}$

Exploratory PD measures to assess the effect of tirzepatide 15 mg versus placebo on glucose infusion related parameters include:

- Area under the glucose infusion rate curve from time of termination of insulin infusion until recovery (PG of 72 mg/dL [4.0 mmol/L]), $AUC_{GIR,PG_nadir-72 \text{ mg/dL}} [\text{mg/kg}]$
 - The time interval from Stop constant insulin infusion (J minutes) to Timepoint 4.0 mmol/L reached (K minutes) is of interest.
- The total amount of glucose infused to attain recovery (PG of 72 mg/dL [4.0 mmol/L]), $G_{\text{tot}} [\text{mg/kg}]$ (i.e. AUC of GIR)
 - The time interval from Start recovery (J+30 minutes) to Timepoint 4.0 mmol/L reached (K minutes) is of interest.
- The proportion of patients who require glucose infusion to attain recovery (PG concentration 72 mg/dL [4.0 mmol/L])
 - If the above calculated $G_{\text{tot}} > 0$, the patient required glucose infusion to attain recovery. If $G_{\text{tot}} = 0$, the patient attained recovery without glucose infusion.

- Average glucose infusion rate [mg/min/kg] from Start plateau 5.5 mmol/L (-30 minutes) to Stop constant insulin infusion (J minutes)
- Average glucose infusion rate [mg/min/kg] from Stop constant insulin infusion (J minutes) to Timepoint 4.0 mmol/L reached (K minutes)

Hypoglycemia recovery parameters

Exploratory PD measure to assess the effect of tirzepatide 15 mg versus placebo on the recovery from hypoglycemia include:

- PG achieved at the end of the spontaneous recovery period
 - This is the PG level at 45 minutes after termination of the insulin infusion (J minutes [Stop constant insulin infusion] + 45 minutes). At $J+45$ minutes, if PG doesn't recover to 72 mg/dL, Start constant glucose infusion.
- The proportion of patients who recovered spontaneously 45 minutes after termination of the insulin infusion ($J+45$ minutes)
- If the PG level at $J+45$ minutes ≥ 72 mg/dL, the patient recovered spontaneously at $J+45$ minutes.

The above other hypoglycemic clamp and recovery exploratory PD parameters (except the proportion of patients who require glucose infusion to attain recovery and the proportion of patients who recovered spontaneously at $J+45$ minutes) will be analyzed in a manner similar to the primary PD analysis using a linear mixed-effect model.

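### SAP 6.9.2.3 applies the trapezoidal rule to pump rates that move in steps and gives no rule for holding a rate between records, so exploratory infusion amounts depend on an unstated data layout

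*SAP*

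**What the plan says.** SAP 6.9.2.3 opens with "AUC will be calculated using trapezoidal rule" and refers to SAP 6.9.1 for calculation details. Section 6.9.1 covers clamp timepoints, hormones, symptom scores, awareness and vital signs, but not the integration of infusion rates. Under 6.9.2.3 the following are AUCs of a rate:

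- G_tot, from J+30 to K
- AUC_GIR from J to K, over each 30-minute plateau, and over recovery
- the insulin amounts from time 0 to I and from time 0 to J

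J is the start of the nadir plateau, when insulin stops. K is the time plasma glucose (PG) reaches 72 mg/dL. A patient with G_tot above zero is coded as one for whom "the patient required glucose infusion to attain recovery", and that status is compared by McNemar test.

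Protocol Appendix 6 describes how rates are recorded. The run-in text reads: "The rates of the variable glucose infusion will be recorded whenever the infusion rate is changed (at least every 30 minutes"). The clamp table has "GIR at least every 30 minutes and every time GIR is changed until time" M. The notes after the table add "Glucose infusion rates will also be captured". In the recovery phase glucose is switched off at J+30, and a constant 5.5 mg/kg/min starts at J+45 if PG has not reached 72 mg/dL. For medical reasons "the constant glucose infusion can be initiated earlier as judged by investigator".

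**The concern.** Recording at each change implies that a rate holds until the next record, so the true profile is a step function. The trapezoidal rule joins successive records by straight lines. Joining 0 at J+30 to 5.5 at J+45 counts glucose during 15 minutes when the pump was off. The 30-minute minimum does not force a record inside that gap.

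The same clamp can therefore yield different G_tot and AUC_GIR values according to how the data set happens to be laid out. The error need not cancel within a patient, because the constant infusion may be needed in one period only or may start at different times in the two periods. A positive area that is pure artefact could also change the yes/no coding of G_tot.

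**Working it through.** The plan states no value for G_tot or AUC_GIR, so there is no figure of its own to reproduce.

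**Inputs from the documents.** Rate 0 from J+30; 5.5 mg/kg/min from J+45 to K; G_tot window J+30 to K; insulin 2.5 mU/kg/min up to J.

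**Assumed.** K = J+50, J+60 or J+75; no restart between J+30 and J+45; the record layouts below.

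**Formula.** Trapezoid minus step sum = 0.5 x sum of (rate jump x gap since the previous record).

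**Ramp at J+45.** With no record since J+30: 0.5 x 5.5 x 15 = 41.25 mg/kg. With 5-minute records: 0.5 x 5.5 x 5 = 13.75 mg/kg.

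**Net error in G_tot.** True value = 5.5 x (K - 45), with K in minutes after J. With records only at changes and zero stamped at K, the error is 41.25 - 0.5 x 5.5 x (K - 45).

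| K | True | Changes only, 0 at K | 5-min records, 5.5 at K | 5-min records, 0 at K | Paired records |
|---|---|---|---|---|---|
| J+50 | 27.5 | 55.0 (+27.5) | 41.25 (+13.75) | 27.5 (0) | 27.5 (0) |
| J+60 | 82.5 | 82.5 (0) | 96.25 (+13.75) | 82.5 (0) | 82.5 (0) |
| J+75 | 165.0 | 123.75 (-41.25) | 178.75 (+13.75) | 165.0 (0) | 165.0 (0) |

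All values are in mg/kg.

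**AUC_GIR, J to K.** Assume 2 mg/kg/min from J+10 to J+30 and K = J+60. True: 2 x 20 + 5.5 x 15 = 122.5. Trapezoid on records at changes with zero at K: 10 + 20 + 41.25 + 41.25 = 112.5 (-8%). With K = J+75: true 205, trapezoid 10 + 20 + 41.25 + 82.5 = 153.75 (-25%).

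**Different start times in the two periods.** Assume J+35 in one and J+45 in the other, with K = J+60 in both. True G_tot: 5.5 x 25 = 137.5 and 5.5 x 15 = 82.5, a difference of 55. With records only at changes and zero at K, both trapezoids equal 0.5 x 30 x 5.5 = 82.5, so the difference vanishes. With 5-minute records laid out alike in both periods, the error is common and the difference stays 55.

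**Coding of G_tot above zero.** Assume unaided recovery at K = J+40 with a new rate r stamped exactly at K. True G_tot is 0. The trapezoid gives 0.5 x r x 10 = 5r with no record since J+30, or 0.5 x r x 5 = 2.5r with 5-minute records.

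**Insulin.** At a constant rate up to J the trapezoid is exact. If the record at J already shows zero, the amount is understated by 0.5 x 2.5 = 1.25 mU/kg per minute of gap before J.

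**The case against.** The strongest reply is that no wrong result has been shown. The error is 0 with paired records, and 0 on a 5-minute grid with zero at K. The eCRF layout and programming specification are not in the two documents, and the SAP names its target plainly as the total glucose infused. A careful programmer could get this right. That stands as a limit on the claim, but the written rule, applied to records as the protocol describes them, does not return the stated target, and correcting it costs almost nothing.

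Four stronger readings might be inferred, and the documents do not support them.

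- *G_tot is overstated by 150%.* The figure is 41.25 / 27.5 for K = J+50. It needs 5.5 carried forward to K while no rate is carried forward from J+30 to J+45, and the documents do not give that K.
- *Appendix 6 contradicts itself on when the post-recovery infusion starts.* The table's K row has "Time of recovery: PG reaches 72 mg/dL (4.0 mmol/L) Start variable glucose infusion", and the text has "When the assessments are finished, PG will actively be raised to 100 mg/dL (5.5 mmol/L) by a variable glucose infusion". The row covers both the assessments and the infusion, and the text can be read as giving their order. A rate stamped exactly at K is a data-layout risk, not a proven conflict.
- *Insulin amounts are wholly exposed, or wholly immune.* They are exposed only if the record at J shows the stopped rate.
- *The treatment comparison is biased.* The documents give no variance or meaningful difference for G_tot. A common error cancels when start times and layout match in both periods.

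**Conclusion.** The point holds as a minor one. The trapezoidal rule is the wrong default for a rate held between pump changes, and the plan has neither a holding rule nor a statement that changes are stored in pairs. The 41.25 and 13.75 mg/kg ramps follow from the documents' own 0-to-5.5 step, given the record spacing. The net errors rest on the assumed K and on the rate stamped there, and can take either sign.

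Affected are G_tot, AUC_GIR (J to K, plateaus, recovery), average GIR if it is derived from the AUC, and the G_tot coding if a post-recovery rate is stamped at K. All are exploratory. The glucagon and other hormone changes, the time from J to K, symptoms, awareness, vital signs and the PG-based spontaneous recovery at J+45 do not use these areas.

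**What to change.** In SAP 6.9.2.3, replace the trapezoid for infusion rates, glucose and insulin alike, with: *Amount = sum of recorded rate x time to the next recorded change (last rate carried forward), using the rate in force immediately after the window start and immediately before the window end.* If the trapezoid is kept, state that every change is stored as a before/after pair at the same time, which gives the same amounts.

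Either version removes a spurious positive G_tot. Neither settles how a restart for PG below 40 mg/dL counts: such a patient has a true G_tot above zero even if PG then reaches 72 mg/dL with no further glucose. The SAP should say how that case is coded in the measure of glucose needed to attain recovery.

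The integration change costs one SAP sentence and a small programming change, with no new data.

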6.9. Pharmacodynamic Analyses

6.9.1. Pharmacodynamic Parameter Estimation

Hypoglycemic Clamp Procedure Measurements

The clamp procedure will be initiated on Day 79 (clamp run-in period) and the hypoglycemic induction will be performed on Day 80 at the end of both treatment periods. The patient will be asked to attend the clinical research unit at approximately 18:00 hours in the evening of Day 79 and will be served a standardized dinner at approximately 19:00 hours and thereafter will be fasted until the end of the clamp procedure on Day 80.

Pharmacodynamic assessments will include counter-regulatory hormone responses (glucagon, growth hormone, cortisol, adrenaline, and noradrenaline), and responses of insulin and C-peptide before and/or during the clamp, as well as clinical hypoglycemia (hypoglycemic symptom score and hypoglycemia awareness), time to hypoglycemia recovery, vital signs during induced hypoglycemia, and other hypoglycemic clamp and recovery parameters.

During the hypoglycemic clamp, for safety considerations, if the target PG concentrations are not achieved within 30 minutes of completion of the previous step, a higher PG concentration will be accepted as the PG concentration at which assessments are conducted. In case PG nadir 45 mg/dL (2.5 mmol/L) target cannot be reached or symptoms of hypoglycemia are unacceptable, nadir at a higher PG concentration will be accepted (decision will be made by site personnel conducting the test) and data will be included in the analyses.

Hypoglycemic clamp

Clamp interventions are based on the mean PG reading (recorded in eCRF) as one blood sample will be measured twice. The actual times (24 hour clock) of each stage of clamp procedure for each patient are provided through eCRF. These actual times, corresponding to key clamp timepoints (see [Table GPHG.3](#) for details) will be identified by programming.

Table GPHG.3. Key Timepoints of Hypoglycemic Clamp Procedure On Day 80

Clamp PG Level	Planned Key Timepoints	eCRF Clamp Procedure Stage Comment
100 mg/dL (5.5 mmol/L)	-30 minutes	Start plateau 5.5 mmol/L
End of 100 mg/dL (5.5 mmol/L)	0 minutes	Stop plateau 5.5 mmol/L
Reaching 63 mg/dL (3.5 mmol/L)	I minutes	Start plateau 3.5 mmol/L
End of 63 mg/dL (3.5 mmol/L)	I +30 minutes	Stop plateau 3.5 mmol/L
Reaching 45 mg/dL (nadir; 2.5 mmol/L)	J minutes	Start plateau nadir Stop constant insulin infusion

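### SAP 6.9.2.3 ends the 63 mg/dL insulin interval at a label and a symbol that conflict (I versus J), and gives no rule for clamps whose plateau began before the target was reached

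*SAP*

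**What the plan says.** SAP 6.9.2.3 describes the constant-rate phase. From the end of the 100 mg/dL plateau to the start of the nadir plateau, "insulin is infused at a constant flow 2.5 mU/kg/min, based on the patient body weight at Day 78 predose of each period". For the exploratory parameters, "AUC will be calculated using trapezoidal rule". The same paragraph fixes the symbols: "I minutes [Start plateau 3.5 mmol/L], and J minutes [Start plateau nadir, Stop constant insulin infusion". Table GPHG.3 in SAP 6.9.1 agrees, setting the eCRF stage "Start plateau 3.5 mmol/L" against I.

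Two insulin amounts are then defined. For 63 mg/dL: "The time interval from Stop plateau 5.5mmol/L (0 minutes) to Start plateau 3.5mmol/L (J minutes) is of interest". For 45 mg/dL: "The time interval from Stop plateau 5.5mmol/L (0 minutes) to Start plateau Nadir (J minutes) is of interest". Both go into a linear mixed-effect model of the kind used for the primary endpoint.

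Protocol Appendix 6 allows a plateau to start before its target is reached. Under its safety considerations, the 63 mg/dL "assessment plateau will be initiated in any case 30 minutes after the end of the assessment plateau at 100 mg/dL". The footnote to the clamp table defines I as the time 63 mg/dL is reached "or 30 minutes after the end of the 100 mg/dL (5.5 mmol/L) assessment plateau, whichever is sooner". The 45 mg/dL step has a matching 30-minute rule, and a higher nadir may also be accepted when symptoms are unacceptable. SAP 6.9.1 keeps the data from such clamps in the analyses.

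**The concern.** The first insulin bullet is an operative endpoint definition. It names one time point in words and a different one by symbol. Followed by symbol, two planned endpoints collapse into one variable and the 63 mg/dL result is wrong.

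The second issue is independent of the letter. Because the rate is constant, each amount is simply elapsed time multiplied by 2.5. When a plateau begins before its target is reached, elapsed time measures when the procedure moved on, not when PG arrived. The amount is then a lower bound on what was needed, yet it enters the model as the amount needed. SAP 6.9.2.3 has no flag, censoring rule or subset for this.

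**Working it through.** The documents give no numerical value for either endpoint, so there is no stated result to reproduce. The one related figure checks: 40 IU at 100 IU/mL is 0.4 mL; 0.4 + 99.6 = 100 mL; 40 / 100 = 0.4 IU/mL, the concentration in the SAP's unit conversion.

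**Inputs**
- Rate: 2.5 mU/kg/min, constant from time 0 to J (SAP 6.9.2.3). The trapezoidal rule is exact for a constant rate.
- I is at most 30 minutes (Protocol Appendix 6, clamp table footnote).
- The 63 mg/dL plateau is planned to last 30 minutes (Appendix 6).
- J is at most 30 minutes after that plateau ends (same footnote).

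**Label against symbol**
- Ending at I: amount = 2.5 x I, at most 2.5 x 30 = 75 mU/kg.
- Ending at J: amount = 2.5 x J, which is also the 45 mg/dL amount. J is at most 30 + 30 + 30 = 90, so at most 225 mU/kg.
- Excess from using J: 2.5 x (J - I). With a full plateau, J - I lies between 30 and 60 minutes, so the excess is 75 to 150 mU/kg.
- Ratio: J / I is at least (I + 30) / I, which is at least 2 because I cannot exceed 30.

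The times below are assumed, to show the range:

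| I (min) | J (min) | 2.5 x I (mU/kg) | 2.5 x J (mU/kg) | Excess (mU/kg) |
|---|---|---|---|---|
| 10 | 70 | 25 | 175 | 150 |
| 20 | 70 | 50 | 175 | 125 |
| 30 | 70 | 75 | 175 | 100 |
| 30 | 90 | 75 | 225 | 150 |

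**Target not reached when the plateau begins (J already corrected to I)**
- Time-out at the 63 mg/dL step: nominal amount 75 mU/kg, whatever was truly needed.
- Time-out at both steps: nominal amount 225 mU/kg for 45 mg/dL.
- Patient timed out at 63 mg/dL in both periods: within-patient difference 75 - 75 = 0, whatever the true difference.
- Patient timed out in one period with I = 20 (assumed) in the other: recorded difference 75 - 50 = 25 mU/kg; the true difference is at least that.
- Higher nadir accepted for symptoms: J may fall well before the time limit, so the 45 mg/dL amount may be well below 225 mU/kg. It is still a lower bound, but not one at a fixed ceiling.

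**What the SAP already separates**
- SAP 6.9.2.1 plans a sensitivity analysis, if deemed appropriate, in patients whose mean PG at J was no higher than 45 mg/dL. It also summarises PG at J by treatment and the frequency of missed nadirs.
- The sensitivity analysis covers the primary glucagon endpoint only. Nothing comparable exists for the insulin amounts, and nothing at all for the 63 mg/dL step.

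**The case against.** The best defence on the symbol is that the words are right. The definition names the start of the 3.5 mmol/L plateau, SAP 6.9.1 says programming identifies key times from eCRF clamp stages, and Table GPHG.3 lists that label as the stage. The same section defines I correctly a few lines earlier, and Protocol 9.6.3 lists two separate targets. A careful programmer would probably use I. That stands, so a reader who infers that the two endpoints *are* identical goes too far: they become identical only if the symbol is followed. The letter should also be confirmed on the signed SAP, since an italic I is easily misread, although I appears correctly elsewhere in the section.

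On missed targets, a reader might infer that timed-out patients never reached the level. Appendix 6 does not support this. After a time-out, glucose is withheld at plateau start so that PG can keep falling, and constant insulin continues until J. PG may reach 63 mg/dL during that plateau. All that is known is that the target was not reached by I or J.

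A reader might also infer a definite bias toward zero. The documents give no time-out frequency, so the size is unknown. With few such clamps it would be negligible, and if within-patient differences run in both directions, capping need not move the mean toward zero.

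Finally, the SAP openly accepts a higher PG, and Appendix 6 records the time to, and PG at, each plateau. Much of the reporting for 45 mg/dL is therefore already planned. What remains open is the 63 mg/dL step and the analysis of both insulin amounts.

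**Conclusion.** The point holds in two limited parts.

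- **Definition.** Label and symbol contradict each other in the 63 mg/dL insulin definition. Programmed by the symbol, the variable duplicates the 45 mg/dL amount and is 75 to 150 mU/kg too large, assuming the 63 mg/dL plateau runs its full 30 minutes. A single fold-error cannot be given, because I and J vary by clamp; with a full plateau the amount is at least doubled.
- **Missed targets.** Clamps whose plateau began before the target was reached contribute a lower bound analysed as an observed value: nominally 75 mU/kg at 63 mg/dL, and 225 mU/kg at 45 mg/dL after two time-outs. This can dilute a treatment difference; how much depends on the number of such clamps under each treatment, which the documents do not give.

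Both variables are exploratory in Table GPHG.1. A reader should not carry either part over to the primary glucagon endpoint or the secondary endpoints, none of which uses these amounts.

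**What to change.** 1. In the 63 mg/dL insulin definition in SAP 6.9.2.3, change J to I.
2. Use the recorded PG at I and J to flag clamps that had not reached 63 or 45 mg/dL, whether through time-out or an early accepted nadir. Report their number by treatment at both steps. For 45 mg/dL the existing rule in SAP 6.9.2.1 can be reused.
3. Keep the mixed model with treatment, period and sequence as the main analysis. Add one sensitivity analysis that either treats flagged amounts as right-censored at the recorded value, with the same fixed effects, or restricts to clamps that reached the target. Two cautions belong in the text: a nadir accepted for symptoms may be informative censoring, and a reached-target subset is selected after randomization, so its result is supportive only.

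The cost is one letter, a flag built from data already collected, and a little extra programming for two exploratory endpoints. No clamp procedure changes.
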